3. STUDY DESIGN

The purpose of the proposed study is to determine whether yoga is an effective method for treating GAD, and its relative efficacy compared to a standard psychosocial intervention. For this purpose, we will conduct a randomized controlled trial. Using superiority tests, yoga (N = 95) will be compared to SE (N = 40), a commonly used control condition. Using non-inferiority tests, yoga will compared to standard CBT for GAD (N = 95). To improve comparisons, all interventions will be conducted in a group format over 12 weekly sessions with 4-6 patients per group and therapists/yoga instructors. We anticipate having approximately 3 yoga instructors, 3 CBT therapists, and 3 SE instructors, along with 2 IEs per enrolling site. All interventions will be conducted at anxiety out-patient clinics in Boston (the Center for Anxiety and Related Disorders at Boston University and the Center for Anxiety and Traumatic Stress Disorders at Massachusetts General Hospital). The third study site, NYU Langone Medical Center in New York City, will not recruit participants and will conduct data analysis and interpretation as well as study oversight. Subjects in all 3 treatment groups will be provided with a credible rationale for the efficacy of their assigned treatment. At each study treatment visit, patients will complete various psychological measures. Some of the study visits require more in-depth assessments involving saliva sample collection, meeting with a study doctor, and a physical examination (see the section 6.1 for more information). The four independent evaluator blinded assessments occur pre-treatment (baseline visit), mid-treatment (Week 6), post-treatment (Week 12), and at a sixmonth follow-up.

The Clinician Global Impression-Severity Scale (CGI-S) and Improvement Scale (CGI-I) [93] will be used in determining remission and response criteria. Treatment response is defined as a CGI-I of 1 (very much improved) or 2 (much improved). Remission is defined as CGI-S of 1 (not at all ill) or 2 (borderline ill). Treatment response will be the primary outcome measure. This allows for a direct comparison with other studies because CGI is the gold-standard measure across clinical trials. Our research team has decades of experience using the CGI, which has excellent psychometric properties and is treatment sensitive [94-97]. Bandelow et al. [94] analyzed clinical trials with more than 5,000 patients with GAD, social anxiety, and depression; the CGI is highly correlated with anxiety and depression scales across disorders.

Trained study clinicians blind to randomized treatment assignment (independent evaluators, IEs) will administer diagnostic assessments and rating scales. All raters will be clinicians who will have undergone specific training to criterion in the use of the study measures (See Integrity of Assessment Procedures in 6.1). To assess for DSM psychiatric diagnoses, study approved independent evaluators (IEs) will use the standard diagnostic intake interviews at each site. These are the Structured Clinical Interviews for DSM-IV and DSM-5 (anticipated to be available in line with enrollment) at MGH and the Anxiety Disorders Interview Schedule (ADIS-5 [92]) at BU. GAD and other diagnostic criteria are identical in the instruments, and DSM-5 is unchanged from DSM-IV for GAD. Each principal investigator has extensive experience with diagnostic interviews, and all raters will be cross certified (see section 6.1 for rater certification and reliability procedures and for assessment details). All clinician rated assessments will be administered by certified blind Independent Evaluators (IEs)

Based on our current study experience, we expect that we will need to screen as potentially eligible twice the number of patients ultimately consenting and that 90% of patients consented will be ultimately enter the randomized phase of treatment after they received a study

diagnostic assessment. We conservatively estimate that 20% of eligible participants will discontinue the intervention prematurely, but all participants who are randomized will be included in the analysis with an intent to treat analytic approach. For ethical reasons, additional treatment will not be withheld for non responders (defined as CGI-I > 2) or anyone for whom additional intervention is indicated in any intervention condition during the 6 month follow up. Non responders (CGI-I>2) at week 12 will be assisted in finding appropriate care from our existing referral resources. All participants will receive 6 month assessments, but any additional treatment received by non responders will be adjusted for in the analyses.

4. SELECTION AND ENROLLMENT OF PARTICIPANTS

4.1 and 4.2 Inclusion and Exclusion Criteria.

All study candidates must meet inclusion criteria and those meeting any of the exclusion criteria below will not be entered into the randomized trial.

Table 1 below lists all inclusion and exclusion criteria.

Table 1: Inclusion and Exclusion Criteria and Rationale.

Inclusion Criteria	Rationale
Male or female outpatients 18 years of age or older with a primary psychiatric diagnosis of generalized anxiety disorder	Population under study
CGI-severity score of 4 or higher	Adequate pre-treatment severity
Off concurrent psychotropic medication for at least 2 weeks prior to initiation of randomized treatment, OR stable on current medication for a minimum of 6 weeks and willing to maintain a stable dose	Treatment confound
Willingness and ability to perform the yoga intervention and to comply with the requirements of the study protocol.	Human subjects concerns
Exclusion Criteria	
Patients unable to understand study procedures and participate in the informed consent process.	Human subjects concern
For women of childbearing age: Pregnant (based on urine pregnancy test), planning to become pregnant, or lack the use of approved methods of birth control	Human Subjects Safety
Serious medical illness or instability for which hospitalization may be likely within the next year	Feasibility, subject safety
Significant current suicidal ideation or suicidal behaviors within the past 6 months	Subject safety
History of head trauma causing loss of consciousness, or seizure disorder resulting in ongoing cognitive impairment	Treatment confound, subject safety
Posttraumatic stress disorder, substance use disorder, eating disorder, or organic mental disorder within the past 6 months	Treatment confound
Lifetime history of psychotic disorder, bipolar disorder, or developmental disorder	Treatment confound
Significant personality dysfunction likely to interfere with study participation (assessed during the clinical interview)	Treatment confound
Prior experience with (more than 5 Yoga classes or CBT sessions within the last 3 years) and/or current practice of mind-body techniques (e.g., yoga, meditation, Tai-Chi, etc) or CBT	Treatment confound
Concomitant psychotherapy for GAD (any psychotherapy)	Treatment confound

Physical conditions that might cause injury from yoga (pregnancy, physical injuries and musculoskeletal problems)

Cognitive impairment (MOCA <21)

Human subjects concern and subject safety Human subjects concern and safety

Equitable Selection of Subjects:

The study population is representative of the population with a primary diagnosis of GAD that stands to benefit from this research. All participants will be adults capable of providing informed consent. We are not excluding any participants based on race, ethnicity, or gender. Participants are selected on the basis of their diagnostic status. Because the use of yoga has not been rigorously tested in pregnant women, those women who are pregnant or not using a reliable form of birth control are excluded from the study. Because the treatment approaches that will be used in this study have never been tested in individuals younger than 18 and might need to be adapted for younger children, children under 18 are excluded from this study. Children between the ages of 18 and 21 will be included. Because a full understanding of the group sessions (yoga, CBT, or SE) is necessary for treatment and sessions will be conducted in English, subjects who are not fluent in English will be excluded from participation.

4.3. Study Enrollment Procedures

SUBJECT RECRUITMENT

Recruitment methods:

Participants will be recruited from patients who present for treatment, are referred or are directly recruited through IRB approved advertisement at the Center for Anxiety and Related Disorders at Boston University (CARD) and the Center for Anxiety and Traumatic Stress Disorders (CATSD) at Massachusetts General Hospital (MGH). Types of recruitment strategies will include advertisements in the media, postings online, particular email services, and clinical referrals.

At MGH, we will be posting information on our own program websites. At MGH, mails and letters will be sent out with a description of our study through the MGH All-User Broadcast and the RSVP for Health program. We will run advertisements in local publications, such as the Metro. We will use the IRB approved CATSD re-contact log (at MGH), Participants who have agreed to be re-contacted in the future will receive emails, letters, and/or phone calls.

Similarly, we will additionally recruit participants for the BU site through postings on our web site, BU's quickie-jobs, and flyers posted at public locations, such as cafes, bookstores, supermarkets, etc. We will further use the IRB approved CARD re-contact log, Participants who have agreed to be re-contacted in the future will receive emails, letters, and/or phone calls.

These recruitment strategies are all aimed at reaching a diverse population.

Individuals who contact our centers will be screened initially by phone for interest in the proposed research, as well as general diagnostic and study eligibility, and interest in research participation. Data for participants who undergo the phone screening process will be deidentified and recorded in the study database phone screening log. Reasons for ineligibility and for non-participation of eligible subjects will be recorded.

Consent and eligibility for randomization procedure:

Interested patients who are eligible for participation will be scheduled for an evaluation meeting where informed consent will be obtained. All potential participants will review the consent form, risks, and benefits associated with the protocol with an approved study investigator and will sign consent prior to completion of any study assessments in this protocol. The study investigator will explain the study, answer any questions, and obtain written informed consent. Participants will be given as much time as needed to review the consent and ask questions prior to participation in study procedures. The study procedures and consent form will be approved by the Institutional Review Board at each of the participating sites prior to study initiation.

Potential participants will undergo formal structured clinical interviews and rating scales (see Assessment section 6.2 for detail) to confirm diagnosis and eligibility. Patients will then undergo safety assessments including medical history, medication use, and laboratory tests, including urine toxicology screen and pregnancy test (for women of childbearing age). In addition, our MD or nurse with MD oversight familiar with the yoga intervention will determine whether the participant is fit for yoga and CBT based on a baseline medical history and physical exam to determine whether study exclusion criteria are met, and any identified medical concerns will be reviewed with signed permission with participant's PCP prior to study entry. We expect to screen and consent approximately 295 individuals such that 230 will meet eligibility criteria and agree to be randomized across the 2 sites.

Randomization Procedure

After eligibility criteria are determined and participants have completed a baseline assessment, and confirmed availability to participate, participants will be randomly assigned to either Yoga, CBT, or stress education (SE) using the variable-sized permuted block randomization procedure (stratified by site).

Our study statisticians will set up the randomization table stratified by site and with variablesized permuted blocks (maximum block size will be 6 to minimize cohort effects). The variablesized permuted block randomization schedules will be generated by [name] (the supervising biostatistician) prior to enrolling the first subject into the study. Randomization will be stratified by site, and groups of 4-6 individuals will be randomized at a time to one of the 3 treatment conditions. Randomizations will be conducted in SAS using the procedures outlined by Efird (2011) [Efird, J. Blocked Randomization with Randomly Selected Block Sizes. *Int. J. Environ. Res. Public Health.*, *8*, *15-20.J.* The randomization code will be emailed by [name] (the trial statistician) to the study coordinator only when the randomization occurs, i.e. once the last participant of each group has completed baseline.

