Yoga for generalized anxiety disorder: A comparison between yoga, cognitive behavioral therapy, and stress education training

Objectives

The general purpose of the study is to determine whether yoga is an effective method for treating GAD, and its relative efficacy compared to a standard psychosocial intervention. Our primary objective is to examine the short-term treatment efficacy of yoga on GAD symptoms. Our secondary objective is to examine the long-term treatment efficacy of yoga on GAD symptoms. Our tertiary objective is to examine and compare the mechanism of treatment changes in yoga and traditional CBT for GAD.

Design and Outcomes

This five-year multi-site study will examine the comparative efficacy of yoga, CBT, and stress education, a previously employed control condition, for patients with GAD. Across 2 enrolling centers (BU and MGH) we will randomize 230 patients with GAD to one of three 12 session weekly study treatments: 12-weekly yoga (n=95), CBT (n=95), or stress education (SE: n=40). Independent clinical assessments will occur before the 12-session intervention phase, at mid-treatment, after the intervention, and at 6-month follow-up. All clinician-rated outcomes will be assessed by trained Independent Evaluators (IEs) blind to treatment assignment. Response (CGI-I of 1 or 2) will serve as the primary outcome measure alongside the SIGH A as the core secondary continuous measure. Secondary outcome measures also include the STAI, PSS, BDI-II and BAI, QOL, ISI, PSQI and PSWQ. The FFMQ, MCQ, pre-ejection period, and cortisol are examined as possible mediators of change. The Credibility/Expectancy Questionnaire will be administered to examine whether credibility and expectancy moderates therapy outcome. In addition, we will explore whether clinical characteristics (comorbid diagnoses) and demographic characteristics (age, sex, SES) are possible moderators. We hypothesize that Yoga and CBT will each be superior to SE at post-treatment FU, and Yoga and CBT will not differ based on equivalency analyses. We predict that treatment changes during yoga are mediated via changes in mindfulness and changes in vagal tone, whereas changes in CBT are mediated via changes in maladaptive cognitions.

Interventions and Duration

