6.2.2 Enrollment, Baseline, and/or Randomization

Enrollment

Participants will be enrolled in the study once they sign the informed consent form. Enrollment will be tracked in the study enrollment log.

Baseline Assessments

For participants who have successfully been screened for eligibility and are enrolled into the study, baseline assessments are performed against which to measure the study outcome. A complete list of the baseline evaluations are presented in Table 6.1.

Randomization

Randomization will precede the intervention.

We will allow a maximum of one month for the time between baseline assessment of participants and randomization; should more than one month pass for logistical reasons, baseline assessments would be repeated prior to randomization. Once participants complete eligibility and are randomized to a group, they will start treatment within 4 weeks.

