6.2.3 Blinding

Independent evaluators will remain blind to treatment assignment throughout the study. To preserve the blind they will be instructed with a reminder script for patients not to discuss their treatment prior to an assessment. The randomization codes will be created by the study statistician prior to entry of the first patient in the trial. Randomization will be stratified only by site. No unblinded analyses will be performed prior to study completion, unless specifically requested by the DSMB, in which case study PIs will only see blinded safety comparisons of the study intervention groups.

The trainers/therapists and the person handling the randomization code cannot be blinded, but they will not be involved in IE ratings, which will be used for outcomes in this trial. The PIs will supervise the treatments, and oversee all study participants including safety and adverse events. The PIs will not, however, know the subject's patient codes and the PIs will not be involved in the independent evaluator ratings. Thus these clinical and oversight study staff will not have access to data and have no influence on the outcome data. Outcome ratings will be completed by the blinded independent evaluators. The data management and analysis will be completed by the study statisticians and data manager who are not involved in clinical treatment or safety assessment at any time.

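### Whole groups of 4-6 go to one arm, but the yoga-CBT non-inferiority test is sized for independent patients and described without a cohort term

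*Combined protocol and SAP*

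**What the plan says.** **Unit of allocation.** Section 4.3 (Randomization Procedure) first says that "participants will be randomly assigned to either Yoga, CBT, or stress education (SE) using the variable-sized permuted block randomization procedure (stratified by site"), which reads as individual assignment. The next paragraph says that the "maximum block size will be 6 to minimize cohort effects" and that "groups of 4-6 individuals will be randomized at a time to one of the 3 treatment conditions". The code is released "once the last participant of each group has completed baseline". Section 6.2.3 adds that "Randomization will be stratified only by site". No allocation ratio is given, and the text does not say whether the maximum of 6 counts patients or groups.

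**Group delivery.** Section 3 has every treatment delivered in groups, with "4-6 patients per group and therapists/yoga instructors". The planned arms are 95 yoga, 95 CBT and 40 stress education (SE).

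**Sample size.** Sections 9.2 and 9.5 take response rates of 57.9% (CBT) and 22.2% (placebo) and a margin of 17.85 points, and arrive at 95 per arm for .80 power. They mention no ICC, design effect or number of cohorts. They describe the test as a comparison of response rates with last observation carried forward.

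**Analysis model.** Section 9.6 puts the treatment cohort at level 3 of the mixed models, but the treatment contrasts it codes are yoga against SE and CBT against SE only.

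**The concern.** Patients who share a room, an instructor and 12 weekly sessions tend to have correlated outcomes. When all of them are also in the same arm, that correlation inflates the variance of the arm's response rate. A calculation for independent patients then overstates power, and a simple two-proportion test gives an interval that is too narrow.

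In a superiority test, a narrow interval produces false claims of difference. In a non-inferiority test it makes it too easy to exclude the margin, so the error runs toward the conclusion that the trial hopes to reach. The plan recognizes the clustering in its models for the comparisons with SE, but the text for the yoga-CBT comparison does not carry it across.

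**Working it through.** **1. Reproduce the stated 95.** Inputs from section 9.2: p = .579 in both arms and margin M = (57.9 − 22.2)/2 = 17.85 points. (The sentence prints 56.7, which would give 17.25; the printed margin matches 57.9.) The significance level is not stated. One-sided .05 is used because it reproduces the figure; one-sided .025 would need 121.

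- n = (1.645 + 0.842)² × 2p(1 − p) / M² = 6.183 × 0.4875 / 0.03186 = 94.6, so 95.
- Power at 95 = Φ(0.1785/√(0.4875/95) − 1.645) = Φ(2.492 − 1.645) = .801.

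The stated figure is therefore right for independent patients.

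**2. Allow for cohorts.** Design effect DE = 1 + (m − 1) × ICC, with m = 5, the middle of 4-6. The documents give no ICC, so the values below are assumptions.

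- Effective n = 95/DE.
- Power = Φ(0.1785/√(0.4875 × DE/95) − 1.645), for a test that uses the correct variance.
- n per arm for .80 = 95 × DE, rounded up.
- True error of a nominal one-sided 5% test that ignores cohorts = 1 − Φ(1.645/√DE).

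| ICC | DE | Effective n | Power at 95 | n per arm for .80 | True error, unadjusted |
|---|---|---|---|---|---|
| 0 | 1.00 | 95 | .801 | 95 | 5.0% |
| .01 | 1.04 | 91.3 | .788 | 99 | 5.3% |
| .05 | 1.20 | 79.2 | .736 | 114 | 6.7% |
| .10 | 1.40 | 67.9 | .678 | 133 | 8.2% |

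Over m = 4 to 6 and ICC .01 to .10, power runs from .791 to .652. These are normal approximations.

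**3. Comparisons with SE.** At 57.9% against 22.2% with 95 and 40 patients (two-sided .05), power is .98 for independent patients and still .92 at ICC .10 with groups of 5. The problem is confined to the non-inferiority test.

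**4. Which unit does the text imply?** Splitting a batch of 6 patients individually at 95:95:40 gives 6 × 95/230 = 2.48, 2.48 and 6 × 40/230 = 1.04 per arm, too few to form any group of 4-6. In groups of 5, the arms are exactly 95/5 : 95/5 : 40/5 = 19:19:8 cohorts. The release of the code per filled group and the reference in section 6.3 to a cohort that has not filled point the same way.

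**5. Can blocks of at most 6 give the planned arms?** Yes, at either level:

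- Patients: 15 blocks of 3:2:1, 15 of 2:3:1 and 10 of 2:2:1 give (45 + 30 + 20) : (30 + 45 + 20) : (15 + 15 + 10) = 95:95:40.
- Cohorts at one site: two blocks of 3:2:1, one of 2:3:1 and one of 2:2:1 give 10:9:4. The mirror image at the other site gives 9:10:4. Together they make 19:19:8.

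**The case against.** The best defense has three parts.

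*The allocation is workable and the sample size is correct.* A reader might infer that blocks of at most 6 cannot deliver 95:95:40, and that the arms would come out equal at about 77 each or as 92:92:46. The documents do not support this. They state no ratio, so those are designs the protocol never describes, and step 5 reaches the planned arms exactly within the limit, with every arm in every block. Nor does the 95 depend on the block rule: it follows from the stated rates and margin. This part of the defense stands in full.

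*The unit is clear enough.* Most of the text points to cohorts, and the general sentence about participants can be read loosely. This largely stands, but the two paragraphs should agree. The power point does not depend on it, because delivery in groups would induce clustering even if patients were assigned individually.

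*Clustering is already in the model, and its size is unknown.* Section 9.6 has the cohort level, and a yoga-CBT contrast could be formed from the two coded contrasts. That is true, and it makes the fix easy. But sections 9.2 and 9.5 do not say that the non-inferiority test comes from that model. They describe response rates with last observation carried forward, and the margin is in percentage points, a scale that a logistic model does not give directly. The cohort level also does nothing for the sample size. It is fair that at ICC .01 the loss is trivial.

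**Conclusion.** The point holds for the yoga-CBT non-inferiority test. The plan allocates whole groups and acknowledges cohort clustering, but sizes this test for independent patients and describes it without a cohort term.

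Any positive ICC of material size takes power at 95 per arm below .80: about .79, .74 and .68 at ICCs of .01, .05 and .10 with groups of 5. Run as described, the test has true one-sided error of about 5.3%, 6.7% and 8.2%, in the direction of declaring non-inferiority. These figures rest on an assumed ICC, cohorts of 5 and an inferred one-sided 5% level.

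It would go too far to conclude that the randomization rule is unworkable, that the arm sizes are wrong, or that clustering is ignored throughout. What is missing on allocation is a statement of the unit and the block composition.

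**What to change.** 1. **Section 4.3.** State that the cohort is the unit of allocation and reword the sentence on individual participants to match. Say that the block maximum of 6 counts cohorts; the rule itself can stay.
2. **Block composition.** Specify one that yields 19:19:8 cohorts, for example 3:2:1, 2:3:1 and 2:2:1 blocks totalling 10:9:4 at one site and 9:10:4 at the other. Fix the number of each block type per site and randomize only their order, so that the totals are met.
3. **Sections 9.2, 9.5 and 9.6.** Run the yoga-CBT non-inferiority test with the cohort effect included, either as a contrast from the level-3 model expressed as a difference in response proportions, or as a cluster-adjusted risk difference. State its one-sided level.
4. **Section 9.2.** Restate power at 95 per arm with an assumed ICC, its source and the design effect, and show a range.

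The cost is revised text, a randomization list that matches it, a slightly lower stated power and wider intervals. No patients need be added, and the arms stay at 95, 95 and 40.
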